### **10.8.2. Number and Percentage of Subjects Who Are Attack Free**

The following attack free endpoints will be derived for each treatment period (the entire dosing period, and the effective dosing period ):

- The number and percentage of subjects who report no attacks during the treatment period for the FAS set and PP population. Subjects who report no attacks and discontinued before the end of the planned treatment period (day 28) are considered attack free.
- The number and percentage of subjects who report no attacks during the treatment period for the FAS set and PP population excluding subjects who discontinue before the planned treatment period (day 28).
- The number and percentage of subjects who report no attacks during the treatment period for the FAS set and PP population. Subjects who discontinue before the planned treatment period (day 28) are considered not attack free.

The above attack free endpoints will also be derived for the entire study period.

### **10.8.3. Number and Percentage of Attack-Free Days**

The number of attack-free days is the sum of the days during the dosing period for which a subject reported no attacks.

The percentage of attack-free days is derived as the total number of days during the dosing period for which subjects reported no attacks divided by the duration of the treatment.

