#### **5.3.3.1. Interim Safety Results**

Overall, once daily dosing of BCX7353 up to 350 mg for 28 days was well tolerated. There were no SAEs reported in Parts 1 or 2 of the study, no Grade 4 TEAEs, and no TEAEs leading to death. The majority of TEAEs were Grade 1 in severity. Three subjects experienced 7 Grade 3 TEAEs, all in the 350-mg dose arm: constipation, abdominal pain, nausea, vomiting, alanine aminotransferase (ALT) elevation, gastrointestinal infection and migraine. Three subjects discontinued study drug due to an AE, all in the 350-mg dose arm: Grade 3 abdominal pain and vomiting, Grade 1 liver disorder, and Grade 3 ALT elevation.

Gastrointestinal-related AEs (primarily mild in severity) were reported more frequently in the 350-mg arm suggesting a dose response. Some GI events, namely nausea and abdominal pain, are also hallmarks of abdominal HAE attacks which were reported more commonly in the 350-mg dose arm (see Section 5.3.3.3 below). It is possible that subjects may have mis-attributed GI TEAEs as abdominal attacks. The incidence of GI events as well as abdominal attacks decreased in the 2 lower dose cohorts compared to the 350-mg dose cohort.

In addition, liver transaminase elevations were noted primarily in the 350-mg dose arm, but may have been confounded by both baseline elevated ALT and AST as well as a much higher rate of past and/or recent androgen use, neither of which were controlled for in the study. No drug rashes were reported in HAE patients as of the interim cutoff. No QTcF increase from baseline or absolute QTcF interval was considered clinically significant, and no TEAEs of arrhythmia were reported.

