#### **10.6. Treatment Period For Efficacy Analyses**

There are 2 treatment periods for efficacy analyses.

1. The entire dosing interval (Days 1 to 28 inclusive) is the date of first dose to the last dose on day 28+24hours, or 24 hour post last dose of the study drug, whichever is earlier.
2. The steady-state or effective dosing interval (Days 8 to 28 inclusive) is the date of first dose +7 days to the last dose on day 28+24hours, or 24 hour post last dose of the study drug, whichever is earlier.

HAE attacks that occur during the treatment period will be included in all relevant efficacy data summaries.

HAE attacks that occur prior to or after the treatment period will also be summarized for the following periods: Qualification Period, screening to baseline Period and the follow-up period.

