#### **10.8. Derived Attack Endpoints**

Subject-reported attacks will be adjudicated by the independent Clinical Endpoint Adjudication Panel (CEAP). The attacks that have been confirmed by the adjudication committee will be included in efficacy analyses. The details of adjudication are provided in the CEAP charter.

The attack endpoints described in this section are based on confirmed attacks by the CEAP, however the rate of attacks will also be calculated for all subject reported attacks. Efficacy analyses will be conducted for HAE attacks reported over the entire dosing period (Days 1 to 28

inclusive), during the dosing period in which BCX7353 should be at steady-state conditions (Days 8 to 28, inclusive), and during the entire study period (Day 1 to the last HAE diary in the follow-up period).

The efficacy analyses will be calculated for 3 treatment periods:

- Entire Dosing Period  
Duration (days) = 28 or (Date of last dose –date of first dose+1), whichever is earlier
- Effective Dosing Period  
Duration (days) = 21 or (Date of last dose –date of first dose-6), whichever is earlier
- Entire Study Period  
Duration (days) = Date of last HAE Attack Diary collection during the follow-up –date of first dose

All efficacy analyses will also be run by treatment period and population (FAS or PP).

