#### 12.1.4. Analysis of Secondary Efficacy Endpoints

The number and percentage of attack-free days will be analyzed similarly to the attack rate endpoint. The secondary efficacy endpoints including attack location, duration, symptoms of attacks, and number and percent of attacks requiring attack medication will be summarized for each treatment group.

The between-treatment comparisons for the weekly attack rate will be also be performed separately by attack location (peripheral or abdominal) using the ANCOVA model as described for the primary endpoint.

The attack onset relative to the time of last dose of study drug, discontinuations due to lack of efficacy and number of emergency room visits and/or hospitalizations will also be reported by treatment group.

AAS will be summarized descriptively by treatment group for each AAS question at attack level and at subject level. The most severe response from all confirmed attacks will be used at subject level summary. The between treatment group comparisons for the total AAS score and individual AAS question scores will be performed using an ANCOVA model. The adjusted qualifying attack rate will be included as a covariate.

The following additional efficacy analyses will also be performed:

- The attack rate in the pre and post treatment periods
- Time intervals between attacks

Time intervals between attacks will be derived as follows:

Subjects with no attack: Interval = duration of treatment or 28  
Subjects with 1 attack: Interval = the Max of the duration of (the first dose to start of the attack) or (stop of attack to the end of the dose )

Subjects with >1 attack: Interval = the duration between the stop of the first attack and start of the next attack (subjects with N attacks will have n-1 intervals)

- Time to first attack after the study medication

The time to first attack after the first study medication will be summarized descriptively and graphically using Kaplan-Meier method. The Kaplan-Meier (KM) estimate for the median, and the first and third quartiles will be determined along with approximate 95% confidence intervals. Brookmeyer-Crowley method will be used for the confidence interval calculation. Subjects who do not have an attack will be censored at the date of last dose for the KM analysis.

- Time to first attack after the last dose

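### The number of attack-free days compared between arms is an unscaled count that stops at the last dose, so days after early stopping score like attack days

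*SAP*

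**What the plan says.** SAP 10.8.3 gives two versions of the endpoint. The count is a plain sum: "The number of attack-free days is the sum of the days during the dosing period for which a subject reported no attacks". The percentage takes the days "for which subjects reported no attacks divided by the duration of the treatment".

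The window for both is the dosing period. SAP 10.6 closes it at the Day 28 dose plus 24 hours, "or 24 hour post last dose of the study drug, whichever is earlier". SAP 10.8 sets its length: "Duration (days) = 28 or (Date of last dose –date of first dose+1), whichever is earlier".

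SAP 2.2.1 and 12.1.1 list the count, not the percentage, among the descriptive statistics for the primary endpoint. SAP 12.1.4 goes further: "The number and percentage of attack-free days will be analyzed similarly to the attack rate endpoint". That means ANOVA and ANCOVA of each dose against placebo and between doses. Tables 14.2.1.19 and 14.2.2.19 are planned for the count, and Tables 14.2.1.20 and 14.2.2.20 for the percentage.

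The attack-interval summary in SAP 12.1.4 has a related rule: "Subjects with no attack: Interval = duration of treatment or 28". With one attack, the interval is the longer of the gap before it and the gap from its end to the end of dosing. With more than one attack, only the gaps between attacks are used.

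On stopping, Protocol 5.3.3.1 reports: "Three subjects discontinued study drug due to an AE, all in the 350-mg dose arm".

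**The concern.** A raw sum over a window that closes at the last dose gives zero to every day after early stopping. An attack day also scores zero, so the count mixes attack control with time on drug. If stopping differs between arms, a between-arm test on the count is biased against the arm with more of it, whatever the drug does to attacks.

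Elsewhere the SAP handles stopping explicitly. SAP 10.8.1 divides the attack rate by duration, SAP 10.8.2 gives three rules for attack-free status in discontinuers, and SAP 12.1.3 gives missing-diary scenarios for the attack rate. The count of days has no such rule, and the SAP does not say which version governs if the count and the percentage disagree.

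**Working it through.** **Plan's own figure.** The documents give no planning figure for attack-free days. SAP Table 2 supplies attack rates for an illustration: 0.7/week (SD 0.45) against 0.3/week (SD 0.3), 18 per arm, stated power 86%. Root-mean-square SD = √[(0.45² + 0.3²)/2] = 0.382; noncentrality = 0.4/(0.382 × √(2/18)) = 3.14; two-sided t-test power at 0.05 = 86.2%. It reproduces.

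**One subject.** An attack-free subject whose last dose is on day d scores d. A completer reaches the same count with 28 − d attack days.

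| Stop day | Count | Completer's attack days for the same count | Percentage: stopper / completer |
|---|---|---|---|
| 7 | 7 | 21 | 100% / 25% |
| 14 | 14 | 14 | 100% / 50% |
| 21 | 21 | 7 | 100% / 75% |

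In the effective period SAP 10.8 gives last dose − first dose − 6 days, so a Day 10 stopper can score at most 9 − 6 = 3 of 21.

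**One arm.** Inputs: 3 AE discontinuations (Protocol 5.3.3.1) among 18 subjects at 350 mg (Protocol 5.3.3). Assumptions: all three stop on the same day d, and a fraction f = 0.75–1.0 of the lost days would have been attack-free. As a check on f, Protocol 5.3.3.3 implies 0.898 − 0.384 = 0.514 attacks/week at 350 mg; with 3-day attacks f = 1 − 0.514 × 3/7 = 0.78.

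Loss in arm mean = 3/18 × (28 − d) × f:

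- Day 7: 3.5 × f = 2.6 to 3.5 days
- Day 14: 2.33 × f = 1.75 to 2.33 days
- Day 21: 1.17 × f = 0.9 to 1.2 days

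**Against the interim benefit.** 0.384 attacks/week × 4 weeks = 1.54 attacks. At an assumed 1 to 3 diary days per attack this is worth 1.5 to 4.6 attack-free days. The loss is then between 0.875/4.61 = 19% and 3.5/1.54 = 228% of the benefit.

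**Simulation at the planning rates.** Day-level, 60,000 subjects per scenario, one common rate per arm, fixed attack length, 3 of 18 stopping in the 0.3/week arm, and a placebo arm that completes in full.

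| Attack length | Placebo mean | Active mean, no stopping | Active mean, stop Day 7 / 14 / 21 | True gap | Gap with stopping, Day 7 / 14 / 21 |
|---|---|---|---|---|---|
| 1 day | 25.2 | 26.8 | 23.5 / 24.6 / 25.7 | +1.6 | −1.8 / −0.6 / +0.5 |
| 3 days | 19.8 | 24.5 | 21.5 / 22.5 / 23.5 | +4.7 | +1.7 / +2.7 / +3.7 |

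In the same runs the active arm's percentage stays at 95.7% (1-day attacks) or moves from 87.5% to at most 87.8% (3-day attacks).

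**Attack intervals.** Read as truncated, an attack-free subject stopping on Day 7 gets 7 instead of 28. The 0.3/week arm mean (1-day attacks) goes from 18.4 to 16.4, 17.2 or 17.9 days for stops on Day 7, 14 or 21. At 0.7/week with 3-day attacks it goes from 7.55 to 7.07, 7.45 or 7.56, so the effect is small and vanishes for late stops.

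**The case against.** The strongest reply is that the SAP already contains most of the cure. The percentage is defined in the same section, analysed with the same model and given its own tables. The weekly attack rate, which carries the main comparison of doses, is divided by duration. Every efficacy table is repeated in the PP population, which requires at least 90% of the planned 28 days of drug (25.2 days), so a stopper on Day 7, 14 or 21 is excluded and an included subject loses at most about 28 − 25.2 = 2.8 days. Protocol 13.2.4 states that there are no formal hypotheses. All of this stands and limits the weight of the point. It does not repair the FAS comparison of the raw count, which remains planned with a p-value and no rule for a conflict with the percentage.

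Four stronger readings are tempting but not supported:

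- **The study's dose comparison as a whole is distorted.** The attack rate and the percentage do not carry this fault.
- **Most of the 350 mg benefit is cancelled.** All three stopping on Day 14 with 2-day attacks would give 57–76% (1.75/3.07 to 2.33/3.07), but that is one cell of the 19–228% range. Protocol 5.1 describes symptoms subsiding over 3 to 5 days; at those lengths a Day 14 stop offsets 1.75/7.68 = 23% to 2.33/4.61 = 51%.
- **350 mg is certainly pushed down against placebo.** Only AE-related stopping is reported by arm. Stopping for other reasons, such as lack of efficacy, could fall on placebo and offset it.
- **The attack-interval endpoint has the same fault throughout.** It is only summarised (Table 14.2.3.1.1). Truncation applies directly only to subjects with no or one attack, and with more attacks stopping can even raise a subject's value. The rule for subjects without an attack also does not say which of its two durations applies.

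**Conclusion.** The point holds for the between-arm analysis of the raw number of attack-free days in the FAS. Under the SAP's definitions, days after early stopping count the same as attack days, which biases the comparison against an arm with more early stopping. With the interim's 3 of 18 AE discontinuations at 350 mg, that arm's mean would fall by about 0.9 to 3.5 days for stops between Day 21 and Day 7. That rests on assumed stop days, on 75–100% of the lost days being attack-free, and on no offsetting stops elsewhere. The direction against placebo is likely from the AE data but not established. The weekly attack rate and the percentage are unaffected in this way, and the PP repeat is largely protected. For attack intervals the issue is an ambiguous definition and uncensored intervals in a descriptive table, for subjects with no or one attack. This should be corrected, but it does not threaten the main result.

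**What to change.** - **SAP 10.8.3 and 12.1.4:** keep the raw count as a descriptive summary only. Base between-group inference on the percentage of attack-free days, or equivalently on days per 28 (per 21 for the effective period); the two differ only by a constant.
- **Supportive analysis:** count attack-free days over a fixed 28 days from first dose, on or off drug. Protocol 8.3.2 asks subjects who stop drug to complete all scheduled visits and procedures, and the diary runs to follow-up, so most of these days should be observed. State a rule for missing diary days.
- **Attack intervals (SAP 12.1.4):** say that the earlier of treatment duration and 28 days applies to subjects without an attack. For subjects with no or one attack, treat an interval that ends at the last dose as censored.

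The cost is SAP wording and minor reprogramming, with no new data. Protocol 13.2.4 plans ANOVA and ANCOVA for continuous efficacy variables, so the move of the count to descriptive status should be recorded. The downside is that scaled values for subjects with short exposure are noisy and can reach 100% after a few days; the fixed 28-day count is the check on that.

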### **10.8.4. Attack Duration**

The duration of each confirmed attack will be calculated in hours, based on the start and stop date and time of the attack. For a confirmed attack that includes more than one subject-reported attack, the duration is calculated from the start of the first subject-reported attack to the end of the last subject-reported attack.

### **10.8.5. Attack Onset Relative to Prior Dose of Study Drug**

For each confirmed attack, the time to attack onset from the time of the prior dose of study drug reported in the subject CRF page will be calculated. If there is no dosing time reported for the dose taken prior to the attack, the attack will not be included in the attack onset analyses.

### **10.8.6. Angioedema Activity Score (AAS)**

The basis of Angioedema Activity Score (AAS) (Weller, Groffik et al. 2013) consists of 5 questions to be answered for each day during which a subject experiences an HAE attack. However, in this study, the answers to the following 4 questions will be collected for each attack:

1. How severe was the physical discomfort caused by this attack, swelling episode or HAE symptom?

2. Were you able to perform your daily activities during this attack, swelling episode, or HAE symptoms
3. Did you feel your appearance was adversely affected by this attack, swelling episode, or HAE symptoms
4. How would you rate the overall severity of this attack, swelling episode, or HAE symptoms

A score between 0 and 3 (inclusive) will be assigned to the responses for each question, and the total score for each confirmed attack will be derived as the sum of the 4 question scores. If more than 2 patient reported attacks are combined as 1 confirmed attack, the most severe response to each individual AAS question will be used for the confirmed attack.

#### **10.8.7. Attack HAE Medications**

All HAE medications reported taken for a confirmed attack will be included in the analyses.

#### **10.8.8. Attack Symptoms**

All symptoms reported for a confirmed attack will be included in the analyses.

#### **10.8.9. Attack Triggers**

All attack triggers for a confirmed attack will be included in the analyses.

#### **10.8.10. Attack Location**

All anatomical locations of swelling reported for a confirmed attack will be included in the analyses.

## 11. STUDY POPULATION

### 11.1. Subject Disposition

A summary table will be generated to provide the following:

- Number of subjects screened
- Number and percentage of screening failures
- Reason for screening failure
- Number and percentage (based on subjects randomized) of subjects in the RS population
- Number of subject randomized and not treated
- Number and percentage (based on subjects randomized) of subjects in the Safety population
- Number and percentage (based on subjects randomized) of subjects in the FAS population
- Number and percentage (based on subjects randomized) of subjects in the PP population
- Number and percentage (based on subjects randomized) of subjects in the PK population
- Number and percentage (based on subjects randomized) of subjects in each PD population

Subject status at study completion will be listed and summarized. The listing will include whether subjects discontinued from the study drug and study and the reasons for the discontinuation of study drug, along with the date of first and last dose and the date of completion or discontinuation from the study drug and study. A summary table will be generated to show:

- Number and percentage of subjects in the Safety population who completed the study
- Number and percentage of subjects in the Safety population who discontinued the study
- Number and percentage of subjects in the Safety population who completed the study drug
- Number and percentage of subjects in the Safety population who discontinued the study drug
- Reason for discontinuation of study drug
- Reason for discontinuation of study

A CONSORT diagram will be created based on the summary tables for the study report.

## **11.2. Protocol Deviations**

Subjects who were randomized but did not satisfy all inclusion and exclusion criteria will be listed. A listing of subjects for whom the treatment blind was broken during the study will also be provided, if appropriate. Subjects with dosing compliance <80% will be considered to have a major protocol deviation. Additional protocol deviations will be reviewed in a data review meeting to classify protocol deviations based on BioCryst Classification of protocol deviation Memo, and to discuss any statistical analysis issues.

## **11.3. Potential Revisions to the SAP**

Potential revisions to the SAP include the refinement of the following: computational algorithms, rules for handling missing or otherwise unclear data, population definitions, and protocol deviations. Statistical methods may be modified if the underlying assumptions of intended methods are violated upon inspection at or before the Data Review Meeting. All revisions will be reported in the study report.

## **11.4. Demographic and Baseline Characteristics**

### **11.4.1. Demography**

The Safety, FAS and PP populations will be the primary populations for analyses of demographics. Demographics, including age, gender, race, ethnicity, weight, height, and body mass index (BMI) will be listed and summarized.

Body mass index (kg/m^2) will be calculated using the standard formula:

$$\text{BMI (kg/m}^2\text{)} = \text{Weight (kg)} / [\text{Height (m)}]^2$$

### **11.4.2. HAE and HAE Medication History**

HAE and HAE medication history will be summarized for the following where possible:

- HAE History
- Past on-Demand Treatments of HAE
- Current on-Demand Treatments of HAE
- Past Prophylactic Treatments of HAE

All HAE medical and medication history collected on the CRF will be listed.

### **11.4.3. Medical History**

Medical history will be listed.

#### **11.4.4. Physical Examination**

Physical examination will be listed.

#### **11.5. Concomitant Medications**

Medications received prior to the date of first dose are considered as prior medications. Medications will be considered as concomitant if the start date of the medication is on or after the date of first intake of study drug or if the start date is prior to the first date of study drug but the medication is ongoing during the treatment period in the study.

Medication verbatim text will be coded using the World Health Organization (WHO) Drug Dictionary. Use of non-study medications will be summarized (number and percentage of subjects) by treatment and WHO preferred name. Multiple drug use (by preferred name) will be counted once only per subject. No inferential statistics will be provided.

Medications that were used for HAE related indications will be summarized separately (plasma-derived C1-INH Berinert, Cinryze will be combined together). Medication data will be listed.

## **12. EFFICACY ANALYSES**

The efficacy data will be summarized descriptively using the FAS and PP populations. Placebo subjects will be pooled across study parts for the final analyses. An overall summary by treatment group will be provided for each dosing period (i.e., entire and effective) defined in section 10.8 to show:

- Number and percentage of subjects who reported at least 1 attack (non-adjudicated), and total number of subject reported attacks
- Number of and percentage of subjects who reported at least 1 confirmed attack , and total number of confirmed attacks
- Number of and percentage of subjects who reported at least 1 confirmed attack that required treatment, and total number and percentage of confirmed attacks that required treatment
- Number of and percentage of subjects who reported at least 1 confirmed attack that did not require treatment, and total number and percentage of confirmed attacks that did not require treatment

Inferential comparisons of the efficacy endpoints will be performed for each BCX7353 dose vs. Placebo and for pairwise dose groups. The FAS and PP populations will be used for the comparisons of efficacy endpoints. All efficacy data collected on CRF will be listed. A separate listing will be provided for the derived efficacy endpoints.

